10.2. Study Periods and Visits

10.2.1 Screening and Washout

10.2.1.1 Screening (Visit 1)

Screening begins after the written informed consent has been obtained from the subject. The purpose of the screening phase is to:

- Ensure that appropriate subjects are entered into the trial
- Determine that the subject meets all eligibility criteria
- Collect demographic and medical data permitting characterization of the subject
- Ensure that prohibited medications are discontinued

To meet these objectives, the duration of screening can be up to 35 days if taper of prohibited medication is required. Subjects continuing to meet all eligibility requirements at Baseline (Visit 2) will be randomized and dispensed double-blinded IP.

All subjects agreeing to participate must give written informed consent using the IRB-approved ICF before any study-related procedures are performed (including tapering of prohibited medications). The ICF will be signed and dated by the subject and Investigator or other appropriate site staff, and a copy of the signed ICF will be given to the subject. The informed consent process will be documented in the source records for each subject.

After the ICF process is complete, a subject number will be allocated by the site, by assigning the next sequential subject number available.

The following procedures will be performed at Screening (Visit 1), which is to occur at least 7 days, but no more than 35 days prior to Baseline (Visit 2):

- Obtain informed consent
- Collect demographic information
- Assign subject number, as described above

- Obtain medical history (including nicotine, alcohol and cannabis use, and menstrual information on women of childbearing potential) and psychiatric history
- Record prior and concomitant treatment and medication use (medication name, dose, and frequency)
- Administer MINI 7.0.2
- Perform physical examination, including height (inches), body weight (pounds), body temperature (°F), and clinical examination of both nasal passages
- Measure vital signs after the subject has rested for 5 minutes: seated systolic and diastolic blood pressure, heart rate, respiratory rate, and body temperature
- Obtain 12-lead ECG
- Obtain blood and urine samples for clinical laboratory examination, including hematology, chemistry, prolactin, thyroid functioning, and urinalysis (refer to Section 10.3.2.1.1 for complete list)
- Obtain urine sample for urine drug screen: Instant Exam to be performed on site, with results thoroughly documented in the source
- For females of childbearing potential, obtain urine sample and complete on-site urine pregnancy test. If positive, a serum pregnancy test should be conducted
- Administer LSAS
- Administer MADRS
- Administer HAM-A
- Administer C-SSRS
- Administer CGI-S
- Review all inclusion and exclusion criteria

10.2.1.2 Washout Period

Subjects requiring washout of prohibited concomitant medications such as benzodiazepines must have stopped taking these medications 30 days prior to Baseline (Visit 2). Selective serotonin reuptake inhibitors, serotonin-norepinephrine reuptake inhibitors, and other antidepressants are allowed so long as the dose has been stable for 30 days prior to Baseline (Visit 2).

Refer to Section 9.7.2 for more information concerning washout procedures.

10.2.2 Baseline (Visit 2)

For subjects continuing to meet all eligibility criteria, the following assessments will be completed at Baseline (Visit 2):

- Subject to fill out ADNM
- Administer MADRS
- Administer HAM-A

- Administer C-SSRS (since last visit)
- Administer CGI-S
- Administer IADQ
- Measure vital signs after the subject has rested for 5 minutes: seated systolic and diastolic blood pressure, heart rate, respiratory rate, and body temperature
- Obtain blood and urine samples for clinical laboratory examination, including hematology, chemistry, prolactin, thyroid functioning, and urinalysis (refer to Section 10.3.2.1.1 for complete list)
- Obtain urine sample for urine drug screen: Instant Exam to be performed on site, with results thoroughly documented in the source
- For females of childbearing potential, obtain urine sample and complete on-site urine pregnancy test
- Record concomitant medication use including the completion of any washout
- Review all inclusion and exclusion criteria

For subjects meeting all study inclusion criteria and no study exclusion criteria, (after review of the assessments above) the following Visit 2 procedures will be performed:

- Randomize the subject and obtain first IP vial
- Train subjects on use of IP and dosing
- Prior to giving a vial(s) to the subject, site staff will identify/mark the vials as vial #1 and vial #2. Staff will then instruct the subject on initial priming and ongoing priming, as outlined in the Study Manual
- Both IP vials will be weighed (as per instructions in the Study Manual). The subject will then complete the initial priming and self-administer the first dose in the presence of site personnel
- Record any AEs reported after IP administration

The next visit (Visit 3) will be scheduled 1 week (± 2 days) after the date of Baseline (Visit 2).

10.2.3 Treatment Period (Visits 3, 4, and 5)

At Visits 3, 4, and 5 the following assessments will be completed:

- Measure vital signs after the subject has rested for 5 minutes: seated systolic and diastolic blood pressure, heart rate, respiratory rate, and body temperature
- Perform clinical examination of both nasal passages
- Administer HAM-A
- Administer C-SSRS (since last visit)
- Administer CGI-S
- Administer CGI-I

- Administer PGI-C
- Returned vials dispensed at the previous visit and new vials will be weighed and dispensed (all weights will be documented in source documents and the eCRF)
- Record concomitant medication use
- Review and record AEs

10.2.4 End of Treatment Period (Visit 6)

At Visit 6, subjects should return to the site with IP vials dispensed at Visit 5. The following assessments will be completed:

- Subject to fill out ADNM
- Administer MADRS
- Administer HAM-A
- Administer IADQ
- Administer C-SSRS (since last visit)
- Administer CGI-S and CGI-I
- Administer PGI-C
- Measure vital signs after the subject has rested for 5 minutes: seated systolic and diastolic blood pressure, heart rate, respiratory rate, body temperature, and ECG
- Perform clinical examination of both nasal passages
- Obtain blood and urine samples for clinical laboratory examination, including hematology, chemistry, prolactin, thyroid functioning, and urinalysis (refer to Section [10.3.2.1.1](#) for complete list)
- Obtain urine sample for urine drug screen: Instant Exam to be performed on site, with results thoroughly documented in the source
- For females of childbearing potential, obtain urine sample and complete on-site urine pregnancy test
- Record concomitant medication use
- Review and record AEs

10.2.5 Follow-up (Visit 7)

At Visit 7, the following assessments will be completed:

- Administer HAM-A
- Administer C-SSRS (since last visit)
- Administer PWC-20
- Measure vital signs after the subject has rested for 5 minutes: seated systolic and diastolic blood pressure, heart rate, respiratory rate, body temperature, and ECG

- Record concomitant medication use
- Review and record AEs

10.3. Assessments

10.3.1 Efficacy Variables

10.3.1.1 Hamilton Anxiety Scale

HAM-A is an established scale to measure the severity of a patient's anxiety. It consists of 14 questions rated on a 5-point scale (0 = not present to 5 = severe). It is completed by trained personnel over a 15-to-20-minute period. The Structured Interview Guide for the HAM-A (SIGH-A) will be used. A copy of the HAM-A is present in Appendix A.

10.3.1.2 Clinical Global Impression Scales

The CGI scale is a clinician-rated scale assessment of the clinician's view of the subject's global health prior to and after participation in a clinical study. The scale assesses the clinician's knowledge of the subject's history, psychosocial circumstances, symptoms, behavior and the effect of these parameters on the subject's capability to function since the last visit with the subject. The CGI consists of 2 components, severity (CGI-S) and improvement (CGI-I). The severity component consists of 1 question that assesses the disease severity of the patient population and is on a scale of 1 to 7 ranging from normal (1) to extremely ill (7). The improvement component evaluates the change of the subject's condition from the Baseline and is on a scale of 1 to 7 ranging from very much improved (1) to very much worse (7). The time frame for rating is the past week.

10.3.1.3 Patient Global Impression of Change

The Patient Global Impression of Change (PGI-C) is a self-administered instrument that measures change in subjects' overall improvement with treatment on a scale where 1 = "very much improved" and 7 = "very much worse."

Very Much Improved	1
Much Improved	2
Minimally Improved	3
No Change	4
Minimally Worse	5
Much Worse	6
Very Much Worse	7

10.3.1.4 Adjustment Disorder New Module Scale

ADNM is a newer scale that has been validated for classification of severity of AjD.⁴⁷ It consists of an 18-item stressful life event checklist and a list of 20 statements about which reactions these types of events can trigger. Subjects are asked to indicate how often the respective statement

applies to them on a 4-point scale (“never” to “often”). For each statement subjects are then asked how long they have been having this reaction (< 1 month, 1-6 months, 6 months-2 years).⁴⁸ A copy of the ADNM is present in Appendix B.

10.3.1.5 International Adjustment Disorder Questionnaire

The International Adjustment Disorder Questionnaire is a recently validated questionnaire to measure AjD symptoms defined by the new International Classification of Disorders (ICD-11) definition.⁴⁸ The subject completes a 9-item checklist of potential stressful events, and if they have experienced any stressful events they then complete a 7-item list of potential problems suffered over the last month (preoccupation symptom) and 3-item list of potential social impacts from the stressors (failure to adapt). A copy of the IADQ is present in Appendix C.

10.3.2 Safety Variables

Safety assessments will include the evaluation of AEs, clinical laboratory assessments, vital signs, 12-lead ECGs, and physical examinations.

10.3.2.1 Clinical Laboratory Safety Assessments

10.3.2.1.1 Clinical Laboratory Tests to be Performed

Samples for the following laboratory tests will be collected at the time points specified in the schedule of events (Table 2-1).

All laboratory tests will be performed on site during the study, and include the following:

Chemistry Panel:	alanine aminotransferase, aspartate aminotransferase, albumin, calcium, chloride, alkaline phosphatase, bicarbonate, cholesterol, creatine kinase, creatinine, direct bilirubin, lactate dehydrogenase, magnesium, globulin, glucose, gamma-glutamyl transferase, indirect bilirubin, phosphorous, potassium, sodium, total bilirubin, total protein, triglycerides, urea nitrogen, uric acid
Hematology/ Hemogram Panel:	hematocrit, hemoglobin, mean corpuscular hemoglobin, mean corpuscular concentration, mean corpuscular volume, platelets, red blood cell count, white blood cell count, red blood cell morphology
Hematology Differential Panel:	basophils, eosinophils, lymphocytes, monocytes, neutrophils
Urinalysis macroscopic panel:	bilirubin, blood, clarity, color, glucose, ketones, leucocyte esterase, nitrite, pH, protein, specific gravity, urobilinogen
Urine Pregnancy Test:	for all female subjects of childbearing potential
Urine Drug Screen:	tricyclic antidepressants, opiates, cocaine, benzodiazepines, amphetamines, barbiturates, cannabinoids, methadone, methamphetamine, phencyclidine, propoxyphene, buprenorphine, ecstasy, oxycodone

- Other:
 - prolactin
 - thyroid stimulating hormone
 - free thyroxine (T4) (if thyroid stimulating hormone is above the upper or below the lower normal limits, then free thyroxine will automatically be performed)

The local laboratory should be used for any unscheduled and follow-up labs, if needed. This includes any confirmatory pregnancy or drug screens for positive urine tests. Additional urine and blood samples may be collected for further evaluation of safety as warranted by the Investigator's judgment.

Results and reports from the local laboratory should be filed with the source documents for each subject. The local laboratory will provide results to the study site staff as soon as they are available and will be provided to sponsor or designated data manager within agreed timelines.

Any laboratory value outside the normal range will be flagged for the attention of the Investigator, who must indicate whether the value is of clinical significance. If the result of any laboratory test performed during Screening (Visit 1) or Baseline (Visit 2) is clinically significant, the subject should not be randomized at Visit 2. However, any abnormal result may be repeated to confirm the finding before excluding the subject from potential inclusion in the study. In addition, subjects should be excluded if they have any other abnormal laboratory test at Screening (Visit 1) that, in the Investigator's judgment, is medically significant in that it would impact the safety of the subject, the conduct of the study, or the interpretation of the study results.

Follow-up/unscheduled laboratory tests may be performed on clinically significant abnormalities as indicated by the Investigator. Unscheduled laboratory tests may be repeated at any time at the discretion of the Investigator for appropriate medical care.

10.3.2.1.2 Specimen Handling Requirements

The transmission of infectious agents may occur through contact with contaminated needles and blood or blood products. Consequently, appropriate blood and body fluid precautions should be employed by all study personnel involved in the collection of blood and handling of specimens in both the clinic and laboratory settings. Refer to current recommendations of the appropriate authorities.

In addition to appropriate handling of subject samples, specific regulations exist regarding the shipment of biologic/etiological samples. Procedures and regulations for the packaging and shipping of infectious samples are outlined in the study laboratory manual or other appropriate reference. The Investigator is responsible for ensuring that all study samples that are to be transported to another location are packed and shipped appropriately according to the applicable regulations.

10.3.2.1.3 Evaluation of Clinical Laboratory Values

The normal ranges of values for the clinical laboratory assessments in this study will be provided by the responsible laboratory and submitted to VistaGen Therapeutics, Inc. prior to the beginning of the study. They will be regarded as the reference ranges on which decisions will be made.

If a laboratory value is out of the reference range, it is not necessarily clinically relevant. The Investigator must evaluate the out-of-range values and record his or her assessment of the clinical relevance in the appropriate eCRF.

All clinical laboratory values that in the Investigator's opinion show clinically relevant or pathological changes during or after termination of treatment must be reported as AEs and followed, as described in Section 11.2.5.

All measurements described in this section are recognized standard methods.

10.3.2.2 Clinical Examinations

10.3.2.2.1 Vital Signs

Vital signs, including heart rate, respiratory rate, and seated systolic and diastolic blood pressure will be measured after the subject has been in a seated position for 5 minutes. Temperature will also be measured.

10.3.2.2.2 Twelve-lead Electrocardiogram

A standard 12-lead ECG will be performed after the subject has been supine for at least 5 minutes. All ECG recordings will be identified with the subject number, initials, date, and time of the recording and will be attached to the subject's eCRF.

10.3.2.2.3 Physical Examination

A complete physical examination (excluding the genitourinary examination) will be performed as indicated in the schedule of events (Table 2-1). The physical examination will include measurement of weight and height, and an examination of the nasal passages.

10.3.2.2.4 Columbia-Suicide Severity Rating Scale

The C-SSRS is a semi structured interview that captures the occurrence, severity, and frequency of suicide-related thoughts and behaviors during the assessment period. The interview includes definitions and suggested questions to solicit the type of information needed to determine if a suicide-related thought or behavior has occurred. The C-SSRS has a "baseline" version which will be completed at Screening (Visit 1) [REDACTED]

[REDACTED] There are a maximum of 19 items to be completed: 7 that are required, 10 potential additional items if there is a positive response to a required item, and 2 items for suicide/suicide behavior present during the interview. The C-SSRS uses dichotomous scales (i.e., yes or no), Likert scales, and text or narrative to further describe the thoughts or behaviors.

10.3.2.3 Adverse Events

The definitions and management of AEs, and any special considerations for AEs, are provided in Section 11.

10.3.2.4 Penn Physician Withdrawal Checklist

The PWC-20 is a 20-item simple instrument for assessing anxiolytic discontinuation symptoms. It consists of 20 questions related to withdrawal from benzodiazepines or other anti-anxiety compounds. The symptoms measured are based on those that are potentially related to anxiolytic withdrawal: gastrointestinal, mood, sleep, motor, somatic, perception and cognition. The questions will cover any symptoms that might occur during the week following discontinuation of PH94B. The PWC-20 scores will be compared between placebo and PH94B.⁴⁹ The PWC-20 is provided in Appendix D.

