	
Interview Guide for the HAM-A (SIGH-A), after 4 weeks of randomized treatment with the study medication
 
4. Population-level summary measure: Difference in mean HAM-A total score between PH94B-treated and placebo-treated subjects after 4 weeks of treatment5. Anticipated intercurrent event: Treatment discontinuation prior to the planned assessment time frame
SAMPLE SIZE DETERMINATION	A sample size of 40 subjects was selected based on information from published studies on treatments for adjustment disorder suggesting that a clinically meaningful effect size could be estimated using a sample size of 40.
STUDY AND TREATMENT DURATION	
The sequence and maximum duration of the study periods will be as follows:
 
1. Screening and washout: [REDACTED]2. Treatment period: From Visit 2 (Baseline) through Visit 6 (End of Treatment)3. Follow-up period: Follow-up visit (Visit 7) conducted approximately 1 week after last treatment 
The maximum study duration for each subject is approximately 10 weeks.
 
The maximum treatment duration for each subject is 4 weeks.

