8.3. Premature Subject Withdrawal

All subjects will be advised that they are free to withdraw from participation in this study at any time, for any reason, and without prejudice. The Investigator should make every reasonable attempt to complete all of the scheduled weekly assessments; with the exception of subjects who withdraw consent to participate in the study. Investigators must attempt to contact subjects who fail to attend scheduled visits by telephone or other means to exclude the possibility of an AE being the cause of withdrawal. Should this be the cause, the AE must be documented, reported, and followed as described in Section [11.2](#).

The sponsor reserves the right to request the withdrawal of a subject due to protocol deviations or other reasons.

The Investigator also has the right to withdraw subjects from the study at any time for the following reasons:

- Any AE, laboratory abnormality, or concomitant illness which, in the opinion of the Investigator, indicates that continued treatment with IP or any other aspect of the study is not in the best interest of the subject
- Disease progression that, in the Investigator's opinion, precludes the subject's continued participation in the study
- Significant non-compliance with the requirements of the protocol or treatment
- The subject misses ≥ 2 consecutive scheduled visits during the 4-week treatment period
- The subject is unable to tolerate study medication based on the Investigator's judgment
- Subject requires PH94B administration more than 4 times per day
- The subject requires a medication prohibited by the protocol (Section [9.7.2](#))
- Termination of the study by VistaGen Therapeutics, Inc.
- At the discretion of the Investigator or VistaGen Therapeutics, Inc.

If a subject is withdrawn before completing the study, the reason for withdrawal and the date of discontinuation will be recorded on the appropriate page of the electronic case report form (eCRF). Whenever possible and reasonable, the evaluations that were to be conducted at the completion of the study should be performed at the time of premature discontinuation.

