Subjects who discontinue early from the study will be asked to return for originally scheduled weekly assessments. If this is not possible, all attempts will be made to have subjects return to the study center to complete the assessments listed for Visit 6 (see Section 10.2.4) as soon as possible. All attempts, including phone or email, to contact the subject must be recorded in the source documents. If the subject fails to respond to those methods, a certified, return receipt letter must be sent to the subject's address indicating that they should contact the study center, with a copy retained in the source documents. Only if all of these attempts fail will it be deemed that the subject is in fact Lost to Follow-up and no final safety data can be collected. No tapering of IP is required in the event of early withdrawal.

Subjects who sign the informed consent form (ICF) and are subsequently withdrawn will not be replaced.

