10.1. Study Duration

The study comprises a screening period of up to 35 days, a double-blind phase of 4 weeks, followed by a follow-up visit approximately 1 week later.

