1. Financial problems (e.g., difficulty paying bills, being in debt).	
2. Work problems (e.g., unemployment, redundancy, retirement, problems/conflicts with colleagues, change of job role).	
3. Educational problems (e.g., difficulty with course work, deadline pressure).	
4. Housing problems (e.g., stressful home move, difficulty finding a secure residence, lack of secure residence).	
5. Relationship problems (e.g., break-up, separation or divorce, conflict with family or friends, intimacy problems).	
6. My own health problems (e.g., illness onset or deterioration, medication issues, injury or disability).	
7. A loved one's health problems (e.g., illness onset or deterioration, medication issues, injury or disability).	
8. Caregiving problems (e.g., emotional stress, time demands).	
9. Some other problem not mentioned above.	

This section should be completed only if you have answered 'Yes' to at least one of the events above. The following statements reflect problem that people sometimes experience in relation to a stressful life event(s). Thinking about the stressful life event(s) you identified above, please indicate **how much you have been bothered by each of the following problems in the past month:**

	Not at all	A little bit	Moderately	Quite a bit	Extremely
10. I worry a lot more since the stressful event(s).	0	1	2	3	4
11. I can't stop thinking about the stressful event(s).	0	1	2	3	4
12. I often feel afraid about what might happen in the future since the stressful event(s).	0	1	2	3	4
13. I find it difficult to adapt to life since the stressful event(s).	0	1	2	3	4
14. I find it difficult to relax and feel calm since the stressful event(s).	0	1	2	3	4
15. I find it difficult to achieve a state of inner peace since the stressful event(s).	0	1	2	3	4
16. Did these problems start within one month of the stressful event(s)?	Yes		No		

	Not at all	A little bit	Moderately	Quite a bit	Extremely
In the past month have the above problems:	0	1	2	3	4
17. Affected your relationships or social life?	0	1	2	3	4
18. Affected your ability to work or your educational life?	0	1	2	3	4
19. Affected any other important part of your life?	0	1	2	3	4

D. Penn Physician Withdrawal Checklist**Penn Physician Withdrawal Checklist**

Did the patient manifest or describe any of the following symptoms since the last visit?

	0 Not Present	1 Mild	2 Moderate	3 Severe

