9.9. Physician Withdrawal Checklist (PWC-20)

Physician Withdrawal Checklist total scores and proportion of subjects with at least one symptom will be derived as described in Section 6.1.7.10. Mean PWC-20 total score will be compared between PH94B- and placebo-treated subjects using a 2-sample t-test. Summaries of PWC-20 total scores and frequency and percentage of subjects with withdrawal symptoms will be presented overall and by treatment group. The difference in total score means, SE of the difference, p-value and 95% confidence interval will be displayed.

10. Other Planned Analysis

No additional analyses are prospectively planned for this study.

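### Protocol 8.3 does not secure a PWC-20 about one week after the last dose for subjects who stop early, and the SAP analyses every score whatever the time since that dose

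*Protocol*

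**What the plan says.** - **Purpose.** Protocol 10.3.2.4 states the target period: "The questions will cover any symptoms that might occur during the week following discontinuation of PH94B". It adds that scores will be compared between the arms.
- **Placement.** "Administer PWC-20" appears in the list for Visit 7 (10.2.5). It is not in the lists for Visits 3 to 5 (10.2.3) or Visit 6 (10.2.4).
- **Recall.** The form in Appendix D asks: "Did the patient manifest or describe any of the following symptoms since the last visit".
- **Timing of Visit 7.** Protocol 10.1 sets it by calendar: "a double-blind phase of 4 weeks, followed by a follow-up visit approximately 1 week later". The synopsis (Study and Treatment Duration) ties it to dosing: "Follow-up visit (Visit 7) conducted approximately 1 week after last treatment".
- **Early stoppers.** Section 8.3 says: "Subjects who discontinue early from the study will be asked to return for originally scheduled weekly assessments". If that is not possible, they are to complete the Visit 6 assessments as soon as they can. The same section also asks, where possible, that "the evaluations that were to be conducted at the completion of the study should be performed at the time of premature discontinuation". Table 13-1 (13.1.1.1) and SAP 3.2 send early stoppers to an Early Termination visit with the Visit 6 measures, and state no visit a week later.
- **Analysis.** SAP 9.9: "Mean PWC-20 total score will be compared between PH94B- and placebo-treated subjects using a 2-sample t-test". It also reports the proportion with at least one symptom. SAP 6.1.5 names the PWC-20 among data that are not windowed and are analysed by nominal visit.

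**The concern.** The checklist measures withdrawal only if its recall period overlaps the first days off drug. For a subject who doses to Visit 6, the schedule achieves this. For a subject who stops earlier, the instructions in 8.3 can place the checklist well after that week, or leave it out, and the SAP has no rule that tells such a score from a properly timed one. A late score mostly reflects background symptoms. Pooled with the others, it pulls the PH94B mean and symptom proportion towards placebo. For a safety measure, a bias towards finding no withdrawal effect is the undesirable direction.

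**Working it through.** **Inputs.** Screening 7 to 35 days (10.2.1.1); treatment 28 days and follow-up about 7 days later (10.1); visits allowed 2 days either side (7.1); 40 subjects randomized 1:1, so 20 per arm (synopsis); target period 7 days after stopping (10.3.2.4); recall since the last visit (Appendix D).

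**The plan's own timeline.** Participation = screening + treatment + follow-up:
- minimum 7 + 28 + 7 = 42 days = 6 weeks
- maximum 35 + 28 + 7 = 70 days = 10 weeks

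This matches the stated 6 to 10 weeks and fixes Visit 7 at nominal Day 35.

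**Early stoppers who keep the original visits.** Assume these include Visit 7 and that Visit 6 (Day 28) is attended, so recall runs over Days 28 to 35. For a last dose on Day s:
- days from last dose to PWC-20 = 35 − s
- days late = (35 − s) − 7
- withdrawal days covered = max(0, min(35, s + 7) − max(28, s))

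| Last dose (day) | Days to PWC-20 | Days late | Withdrawal days covered (of 7) |
|---|---|---|---|
| 7 | 28 | 21 | 0 |
| 14 | 21 | 14 | 0 |
| 21 | 14 | 7 | 0 |
| 22 | 13 | 6 | 1 |
| 24 | 11 | 4 | 3 |
| 26 | 9 | 2 | 5 |
| 27 | 8 | 1 | 6 |
| 28 (completer) | 7 | 0 | 7 |

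Moving Visits 6 and 7 within their windows changes the coverage to 0 to 2 days for a Day 21 stop and 1 to 5 for a Day 24 stop. Stops on Days 7 and 14 stay at 0.

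If Visit 6 is missed and the last visit was Visit 5 (Day 21), recall runs over Days 21 to 35. It then covers 0 days for a Day 14 stop, 4 for a Day 18 stop and all 7 for stops from Day 21 on.

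**Early stoppers who complete only the Visit 6 list.** There is no PWC-20 on that list.

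**End-of-study evaluations at the time of stopping.** If this instruction includes the PWC-20, the subject has been off drug for 0 days.

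**Visit 7 about a week after the last treatment (synopsis).** The PWC-20 falls 7 days after the last dose, or 5 to 9 with the window. The recall wording can still lose days. For a last dose on Day 10 with a visit on Day 14 and the PWC-20 on Day 17, recall since the last visit covers 17 − 14 = 3 of the 7 days.

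**Effect on the comparison.** Let δ be the true mean excess on PH94B in the withdrawal week, and p the fraction of PH94B scores taken too late to reflect it. If late scores have the placebo mean, the expected difference is (1 − p)δ. The documents give no value for p. As an assumption, 1 to 4 such scores among 20 give p = 1/20 to 4/20, a shrinkage of 5% to 20%. Subjects with no PWC-20 do not enter the t-test and so do not dilute it.

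**The case against.** The strongest reply is that the protocol already contains a correct timing. The synopsis places Visit 7 about a week after the last treatment, and 7.1 describes it as following a one-week washout. A site working from that wording would obtain a well-timed checklist. This stands: the defect is a conflict between passages, not an established loss.

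Three further points also stand:
- The schedule of events (Table 2-1) is not in the text available for review, so an early-termination entry for the PWC-20 cannot be ruled out.
- The request for evaluations at the time of stopping may mean the Visit 6 set, as 13.1.1.1, 14.6.1 and SAP 3.2 suggest. A PWC-20 on the day of stopping is only one reading.
- The PWC-20 is not among the listed safety endpoints, and the SAP calls the study exploratory. Adverse events count as treatment-emergent through Follow-up (11.1.5), which is a partial backstop.

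A reader might infer that early stoppers yield no valid withdrawal data at all. The documents do not support this: stops after Day 21 keep part of the week, and the synopsis permits a correctly timed assessment. A reader might also infer that early stoppers are one of the few chances to observe withdrawal. That does not follow either. No taper is described for completers, who stop after the longest exposure and are assessed about 7 days later, so they should supply most of the withdrawal data.

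None of this repairs the analysis. The first instruction in 8.3 still leads to late scores, and SAP 6.1.5 and 9.9 still accept them.

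**Conclusion.** The point holds as a conflict with a definite consequence. If 8.3 is followed by keeping the original visits, a last dose by Day 21 gives a PWC-20 at least 14 days later with none of the 7 withdrawal days covered; last doses on Days 22 to 27 give 1 to 6 days. These are nominal days and assume that Visit 6 is attended. If only the Visit 6 list is completed, the supplied text provides no PWC-20, subject to Table 2-1.

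The SAP treats mistimed and well-timed scores alike, so any excess on PH94B is diluted in the t-test and the symptom proportion. How much cannot be stated: the 5% to 20% range rests on an assumed 1 to 4 late scores among 20. The primary HAM-A analysis is not affected. The point is worth acting on because the correction is cheap and the direction of bias is towards missing a withdrawal effect.

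**What to change.** **Protocol.** Reconcile the synopsis (Study and Treatment Duration), 8.3, 10.2.5, Table 13-1 and SAP 3.2, with Table 2-1 to match, so that the PWC-20 is completed about 7 days after the last dose. For early stoppers who keep attending, use the scheduled visit nearest that point. On nominal weekly visits this always falls 4 to 10 days after the stop: a Day 24 stop uses Day 28 (4 days) and a Day 25 stop uses Day 35 (10 days). Ask about symptoms since the last dose. The least favourable case, 4 days, then covers 4 of the 7 withdrawal days.

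**SAP 6.1.5 and 9.9.** Use only PWC-20 records taken 4 to 10 days after the last dose in the t-test and the proportion, and list the others with days since last dose. A lower limit of 5 days would discard the records collected for stops on Days 3, 10, 17 and 24. SAP 6.1.5 sends unscheduled safety assessments to listings only, so it must also say that a PWC-20 taken at an earlier visit under this rule is eligible for analysis.

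**Cost.** Wording in both documents and one 20-item checklist at a visit already requested. A few scores outside the range, including some moved there by the 2-day visit window, leave the comparison. Subjects who cannot attend scheduled visits may still have no PWC-20.
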